6.4.2. Analysis of PK Variables

Based on PKS, the PK parameters of subjects will be descriptively analyzed by dose group and visit, with the number of subjects, mean, standard deviation, geometric mean, median, quartiles, maximum, minimum, coefficient of variation, and geometric coefficient of variation listed. Non-parametric test will be used to compare T_{max} and T_{max,ss} in each dose group. The power model will be used to assess the dose proportionality between the main PK parameters (C_{max}, AUC_{0-24h}, C_{max,ss}, AUC_{0-24h,ss}) and administered dose, and trend charts related to main PK parameters and administered dose will be provided.

ullet PK indicators: See the table below for details of C_{max} , T_{max} , AUC_{0-24h} , etc. Calculated according to the actual blood collection time (actual blood collection time = actual blood collection date and time - actual administration date and time; the actual blood collection time

before administration is 0 h). For plasma concentration values below the quantification limit (BQL), those before reaching C_{max} will be treated as 0, and those after reaching C_{max} will be treated as missing values

Category	Parameter	Definition
D1 PK Parameters	C _{max}	Maximum plasma concentration, obtained directly from the observed plasma concentration-time data.
	T_{max}	Time to maximum plasma concentration, obtained directly from the observed plasma concentration-time data.
	AUC _{0-24h}	Area under the plasma concentration-time curve from time zero to 24 h (calculation method: Linear up log down).
D28 PK Parameters	C _{max,ss}	Maximum plasma concentration at steady state, obtained directly from the observed plasma concentration-time data.
	$T_{\text{max,ss}}$	Time to maximum concentration at steady state, obtained directly from the observed plasma concentration-time data.
	C _{min,ss}	Minimum concentration over a dosing interval at steady state, obtained directly from the observed plasma concentration-time data.
	AUC _{0-24h,ss}	Area under the plasma concentration-time curve from time zero to 24 h at steady state (calculation method: Linear up log down).
	Cl _{ss} /F	Apparent clearance, $\text{Cl}_{\text{ss}}/\text{F} = \text{Dose}/\text{AUC}_{0\text{-}\tau,\text{ss}}$ (Dose is the corrected administered dose, and the correction formula is dose*(326.47/370.44)), for parent drug only.
	λ_{z}	Elimination rate constant, calculated as the slope of the terminal phase of the plasma concentration-time curve on a semi-log scale using a linear regression method. For 100 mg, 150 mg and 200 mg (alternative) groups only.
	t _{1/2}	Terminal elimination half-life, $t_{1/2} = \ln 2 / \lambda_z$. For 100 mg, 150 mg and 200 mg (alternative) groups only.
	R _{ac} [C _{max}]	Accumulation ratio of C_{max} . $R_{ac}[C_{max}] = C_{max,ss}(multiple)/C_{max}(first)$.
	R _{ac} [AUC _{0-24h}]	Accumulation ratio of AUC. $R_{ac}[AUC] = AUC_{0-24h,ss}$ (multiple)/AUC _{0-24h} (first).

Note: τ is the dosing interval. In this study, $\tau = 24$ h.

Sponsor: Burgeon Therapeutics Co., Ltd.

Protocol No.: BGT-002-004

• For the power model, log transformation will be performed based on PK parameter = $e^{\alpha}(dose)^{\beta}$, and the model after transformation will be $ln(PK parameter) = \alpha + \beta ln(dose) + \epsilon$. The overall slope β , *i.e.* the exponent of the model, will be calculated to estimate its 90%CI.

• Evaluation criteria for the power model: If the 90% CI for β completely falls within the judgment interval, it can be considered that the PK parameter has dose proportionality. If the 90% CI of β falls completely outside the judgment interval, the PK parameter does not have dose proportionality in the given dose range. If the 90%CI of β partially overlaps with the acceptance interval, no definitive conclusion can be made within the given dose range.

- The judgment interval of the power model is $[1 + \frac{\ln(\theta_L)}{\ln(r)}, 1 + \frac{\ln(\theta_H)}{\ln(r)}]$. Where, r=H/L, H represents the highest dose administered and L represents the lowest dose administered; θ_H is the upper limit of confidence interval given based on statistical and experimental experience, and θ_L is the lower limit of confidence interval given based on statistical and experimental experience. In this study, $[\theta_L, \theta_H]$ is [0.5, 2].
- ullet Non-parametric Kruskal-Wallis test will be used for T_{max} and $T_{max,ss}$ of each dose group
 - PK parameters will be listed

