### **Pharmacokinetics**

Based on some available PK data, the exposure of BGT-002 in human plasma demonstrated a good dose dependency after administration of BGT-002 tablets.

As of January 04, 2023, the mean  $C_{max}$  after single doses of BGT-002 at 12.5 mg–300 mg in healthy subjects was 1.61  $\mu\text{g}/\text{mL}$ –48.88  $\mu\text{g}/\text{mL}$ , the  $AUC_{last}$  was 32.4  $\mu\text{g}\cdot\text{h}/\text{mL}$ –2703.12  $\mu\text{g}\cdot\text{h}/\text{mL}$ , the median  $T_{max}$  (25 mg–300 mg groups) occurred at 1.00 h–1.75 h, and the mean  $T_{1/2}$  ranged from 25.0 h–75.1 h. The half-life at single doses in healthy subjects showed a tendency to increase with higher doses.

As of December 08, 2022, a total of 12 subjects (11 males and 1 female) were enrolled in the BGT-002 25 mg dose group of the multiple-dose trial for healthy subjects for 14 consecutive days. The  $C_{max}$  was 14.1  $\mu\text{g}/\text{mL}$  and  $AUC_{0-24h}$  was 257.1  $\mu\text{g}\cdot\text{h}/\text{mL}$  on Day 14 after multiple-dose administration; there were 12 subjects (10 males and 2 females) in the 50 mg dose group. After 14 days of continuous administration, the drug concentration was close to a steady state. On Day 14, after multiple-dose administration, the  $C_{max,ss}$  was 27.1  $\mu\text{g}/\text{mL}$  and  $AUC_{0-24h,ss}$  was 513.9  $\mu\text{g}\cdot\text{h}/\text{mL}$ . The pharmacokinetics exhibited good linearity after continuous administration at 25 mg and 50 mg.

As of January 04, 2023, after administration with a high-fat meal in healthy subjects in the food effect trial, the median  $T_{max}$  was 3.50 h,  $C_{max}$  was 12.18  $\mu\text{g}/\text{mL}$ ,  $AUC_{last}$  was 571.31  $\mu\text{g}\cdot\text{h}/\text{mL}$ , and  $t_{1/2}$  was 41.27 h; after administration under fasting conditions, the median  $T_{max}$  was 1.50 h,  $C_{max}$  was 16.64  $\mu\text{g}/\text{mL}$ ,  $AUC_{last}$  was 579.70  $\mu\text{g}\cdot\text{h}/\text{mL}$  and  $t_{1/2}$  was 41.07 h. After administration following a high-fat meal, the  $T_{max}$  was delayed and the peak concentration decreased slightly, but the degree of drug absorption hardly changed.

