#### ➤ **Dose Ascending Principle:**

- 1) In this trial, it is planned to start with 50 mg as the lowest dose and 200 mg as an alternative dose. A total of 4 to 5 dose groups will be selected from 50 mg, 75 mg, 100 mg, 150 mg, and 200 mg (alternative) groups, and the trial will be gradually carried out according to the above set doses.
- 2) After the investigator and sponsor determine that 50% of subjects in each dose group have good results for 14-day safety evaluations, the trial can proceed to the next dose group. If necessary, subsequent trial protocols may be appropriately adjusted based on previous safety and PK analysis results (such as increasing or decreasing administration observation time or dose).
- 3) If the criteria for termination of dose ascending are met during dose ascending, even if the predetermined maximum dose has not been reached, the dose ascending should be terminated.

	
4) After the maximum estimated dose is reached by dose ascending, the investigator and the sponsor will discuss and analyze the existing safety and PK data before deciding whether to continue the next dose exploration. Any continuation will be subject to the approval of the Ethics Committee.
 
➤ Stopping Criteria for Dose Ascending:
 
Within 14 days after the first dose, if any of the following criteria are met, the investigator and the sponsor will discuss and analyze the reasons and judge the impact on subsequent trials to decide whether to terminate dose ascending:
 
 
1)In the same dose group, more than 1/2 of subjects experience Grade 2 and above AEs related to the study drug; or more than 1/3 of subjects experience Grade 3 and above AEs related to the study drug;
 
2)The trial should be suspended if 1 case of serious adverse event (SAE) related to the study drug occurs during the trial;
 
3)Based on the available PK data, the investigator agrees with the sponsor that there is no need to continue the trial.
 

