3.2. Dose Group Design

It is originally planned to set 3-4 dose groups in this study, and the dose ascending design

is as follows: 50 mg, 75 mg, 100 mg, and 125 mg (alternative). In this trial, it is planned to start with 50 mg as the lowest dose group. During the study, whether to continue to escalate to a higher dose group or adjust the dose ascending ratio will be determined based on available data.

As of September 13, 2023, based on the results of the completed interim analysis for three dose groups (50 mg, 75 mg and 100 mg), after discussion, the Sponsor and investigator decided to add 150 mg and 200 mg (alternative) groups for a 28-day continuous administration study, with 3 sentinels in the 150 mg and 200 mg (alternative) groups, respectively (2 subjects in the test group, and 1 subject in the placebo group) and observe for 8 days. If the safety is good, the remaining subjects will continue to be enrolled in this dose group (7 subjects in the test group and 2 subjects in the placebo group).

Dose (mg)	50	75	100	150	200 (alternative)
Number of Subjects (Study Drug + Placebo)	9+3	9+3	9+3 (Male:female = close to 1:1)	9+3	9+3

Each dose group will randomly include 12 screened eligible subjects with NASH, with 9 taking the study drug orally and 3 taking the placebo orally. A total of 48-60 subjects will be included in the study. Whether to conduct the dose expansion study will be based on the results of the dose ascending phase.

Study Schedule:

	1	Hospitalization (D-1 to D8, D27 to D29)		
Screening Period (D-56~D-1)	Run-in Period (D-56~28~D-1)	Treatment and Observation Period (D1~D29)	Follow-up Period (D30~D56)	

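### Does the SAP's two-fold power-model limit wrongly label non-proportional exposure as dose proportional?

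*SAP*

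**What the plan says.** SAP 6.4.2 (Analysis of PK Variables) regresses the log of each main PK parameter on log dose. The parameters are Cmax and AUC0-24h on D1 and their steady-state counterparts on D28. The overall slope β "will be calculated to estimate its 90%CI".

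The verdict has three outcomes. If the CI lies wholly inside the limits, "it can be considered that the PK parameter has dose proportionality". If it lies wholly outside, proportionality is rejected for the range studied. If it overlaps in part, no conclusion is drawn. The limits for β are 1 + ln(θ)/ln(r), with θ set to 0.5 and 2, and "r=H/L, H represents the highest dose administered and L represents the lowest dose administered". The only basis given for θ is statistical and experimental experience.

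The protocol synopsis (Statistical Analysis, Pharmacokinetic Analysis) calls this work exploratory and also plans the slope with its 90% CI. On earlier data, the protocol's Pharmacokinetics section states: "The half-life at single doses in healthy subjects showed a tendency to increase with higher doses". The same section reports good linearity at 25 and 50 mg after repeated dosing.

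**The concern.** Nothing in the rule asks whether the CI contains 1. Dose-normalised exposure may differ by almost a factor of two between the lowest and highest dose, and the parameter still earns the unqualified label of dose proportionality.

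The protocol seems to show that this could happen. Single-dose AUClast runs from 32.4 to 2703.12 µg·h/mL over 12.5–300 mg, a slope of 1.39, which lies inside the limits for either dose range. If that slope held here, exposure would be 4.6-fold instead of 3-fold at 150 versus 50 mg, and 6.9-fold instead of 4-fold at 200 versus 50 mg. A report of proportional PK would then mislead anyone predicting exposure at the higher doses.

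**Working it through.** **1. Limits from the SAP's formula.** The dose groups come from the protocol's Dose Ascending Principle.
- 50–150 mg, r = 3: 1 ± ln 2/ln 3 = 0.369 to 1.631.
- 50–200 mg, r = 4: 1 ± ln 2/ln 4 = 0.500 to 1.500.

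At either limit r^(β−1) is exactly 2 or 0.5. The margin therefore means the same thing, two-fold, whichever top dose is reached. Neither document states a numeric interval to compare with.

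**2. Slopes in the protocol's own data.** Slope = ln(exposure ratio)/ln(dose ratio), assuming that the ends of the reported ranges belong to the lowest and highest doses.

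| Data | Calculation | Slope | In the SAP model? |
|---|---|---|---|
| Single-dose AUClast, 12.5–300 mg | ln(2703.12/32.4)/ln 24 | 1.39 | No |
| Single-dose Cmax, 12.5–300 mg | ln(48.88/1.61)/ln 24 | 1.07 | Yes (Cmax) |
| Multiple-dose AUC0-24h, 25–50 mg | ln(513.9/257.1)/ln 2 | 1.00 | Yes (AUC0-24h,ss) |
| Multiple-dose Cmax, 25–50 mg | ln(27.1/14.1)/ln 2 | 0.94 | Yes (Cmax,ss) |

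Only the parameter outside the model is steep.

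**3. Is the steepness confined to higher doses?** The food-effect trial's fasted 100 mg AUClast (579.70) splits the range:
- 12.5–100 mg: ln(579.70/32.4)/ln 8 = 1.39.
- 100–300 mg: ln(2703.12/579.70)/ln 3 = 1.40.

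The slope is the same in both halves, and the lower half contains 25–50 mg, where multiple-dose AUC0-24h is linear. The data therefore do not place a departure in the range this trial extends into. The contrast is between metrics and regimens.

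Exposure per mg shows the same. Single-dose AUClast per mg is 32.4/12.5 = 2.59, 579.70/100 = 5.80 and 2703.12/300 = 9.01. Multiple-dose AUC0-24h per mg is 257.1/25 = 10.28 and 513.9/50 = 10.28, already above the 300 mg single-dose value. The single-dose slope cannot simply be carried over to steady state.

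**4. How the rule behaves if the true slope were 1.39.** There are 9 active subjects per dose (SAP 3.2: "with 9 taking the study drug orally and 3 taking the placebo orally"). CI half-width = t(0.95, n−2) × σ/√Sxx, with σ = √ln(1+CV²). Four groups: n = 36, Sxx = 5.804, t = 1.691. Five groups: n = 45, Sxx = 10.848, t = 1.681. The documents give no between-subject CV, so 20–50% is assumed.

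| CV | Pass with CI wholly above 1, four groups | Same, five groups |
|---|---|---|
| 20% | 0.89 | 0.55 |
| 30% | 0.55 | 0.32 |
| 40% | 0.21 | 0.18 |
| 50% | 0.04 | 0.06 |

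(Simulated, 200,000 draws.) These are not false verdicts by the rule's own standard, because 1.39 lies inside the two-fold limits. Requiring a 90% CI within limits amounts to two one-sided tests at 5%, so a slope at or beyond a limit passes at most about 5% of the time.

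**5. What a reader would see.** With four groups, CV 30% and an estimate of 1.392, the half-width is 1.691 × 0.2936/√5.804 = 0.206 and the CI is 1.186 to 1.598. It passes, but the CI stands beside the verdict and plainly excludes 1. Its fold form follows at once: 3^0.186 = 1.23 to 3^0.598 = 1.93. With five groups the CI is 1.242 to 1.542, and the verdict is no conclusion.

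**6. Would another rule be better?** Limits of 0.8 to 1.25 (an assumption; not in the documents) allow β = 1 ± 0.203 for r = 3 and 1 ± 0.161 for r = 4. The half-widths at CV 30% are 0.206 and 0.150. With four groups, a CI of that width fails even when centred exactly on 1. With five groups the estimate must fall within 0.011 of 1. Withholding the label whenever the 90% CI excludes 1 would deny it to about 10% of truly proportional parameters, by the definition of a 90% CI, and would put a difference test inside an equivalence rule.

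**The case for a change.** The strongest contrary case is this. PK is the first secondary objective, and the SAP attaches a formal verdict to an analysis that the protocol calls exploratory. The margin rests on experience alone. AUClast is not irrelevant either: under linear, time-constant kinetics, steady-state AUC over a dosing interval equals single-dose AUC to infinity, so a lengthening half-life is a real signal. The 25–50 mg data only touch the bottom of this trial's range. At a true slope of 1.39, the rule returned a finding of non-proportionality in at most 0.6% of simulated trials.

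Some of this stands. The documents do not show that exposure is proportional from 75 to 200 mg, and the two-fold margin is wide. The label would say more if it named that margin. But the near-absence of a negative verdict at 1.39 follows from 1.39 being inside the margin, so it is the same complaint about width. The linear-kinetics argument does not rescue 1.39 as a forecast, because the protocol's steady-state AUC0-24h is flat per mg.

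The consequence is also missing. The Dose Ascending Principle and the Stopping Criteria rely on review of safety and PK data by the investigator and sponsor; neither mentions the power model. Exposure at each dose used is measured directly, with geometric means by dose group, trend charts and listings already planned in SAP 6.4.2.

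**Conclusion.** The concern does not hold. The arithmetic behind it is right: the limits are 0.369–1.631 or 0.5–1.5, and a CI excluding 1 can pass. But that is how an equivalence rule works. This one is fixed in advance, has an explicit inconclusive outcome, and sits in an exploratory analysis that reports β with its 90% CI.

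The evidence that two-fold is the wrong margin here is one slope, 1.39, for a parameter outside the model. The protocol's figures for parameters in the model give 0.94 to 1.07. How often a pass would coincide with a CI above 1 depends entirely on an assumed CV: if the slope really were 1.39, from 0.89 at 20% down to 0.04 at 50% with four groups. The tighter alternative could hardly ever confirm proportionality with 9 active subjects per dose, and the fold ratio is only a transform of the slope and CI already planned. No change to the plan is needed.

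This rests on the reported range ends belonging to the extreme doses, and on the slope and its CI being reported with the verdict, as both documents plan.

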6.4.3. Analysis of PD Variables

Based on PDS, PD indicators of subjects as well as changes and percentage changes from baseline will be descriptively analyzed by dose group and visit time point, with the latest test result before the first dose as the baseline.

- PD indicators: MRI-PDFF, CAP, LSM, BMI, ALT, AST, TG, LDL, and TC
- Visit time points include baseline, D29 and D56
- Change from baseline = PD indicator of each visit baseline PD indicator; percentage change = change from baseline/baseline PD indicator × 100%
- The proportion of subjects with a relative reduction of at least 30% in liver fat content measured by MRI-PDFF will be listed
- The mean change-time curve and the histogram of mean percentage change from baseline will be plotted for PD indicators by visit time point
 - The PD indicators of enrolled subjects will be listed

6.4.4. Analysis of Exploratory Variables

Based on PDS, exploratory indicators of subjects as well as changes and percentage changes from baseline will be descriptively analyzed by dose group and visit time point, with

the latest test result before the first dose as the baseline.

• Exploratory indicators: CK18, FGF21, IP10, hsCRP, TIMP1, and β -HB (the test indicators will be adjusted according to the actual condition of the testing unit)

- Visit time points include baseline, D29 and D56
- Change from baseline = exploratory indicator of each visit baseline exploratory indicator; percentage change = change from baseline/baseline exploratory indicator × 100%
- The mean change-time curve and the histogram of mean percentage change from baseline will be plotted for exploratory indicators by visit time point
 - The exploratory indicators of enrolled subjects will be listed

6.5. Analysis of Safety

6.5.1. Adverse Events

Based on SS, the number of subjects, number of events and incidence of AEs, AEs related to study drug, Grade \geq 3 AEs, Grade \geq 3 AEs related to study drug, SAEs, SAEs related to study drug and AEs leading to early withdrawal will be summarized by dose group; the relationship between AEs and the study drug, grade of AEs, measures taken for the study drug, measures taken for adverse events and outcome will also be summarized.

- AEs related to study drug refer to AEs judged as definitely, probably or possibly related to the study drug
 - All the AEs will be coded using MedDRA v26.0 or above.
- The number of events, number of subjects and incidence of AEs and AEs related to study drug will be calculated by SOC/PT
- The number of events, number of subjects and incidence of AEs and AEs related to study drug will be calculated by SOC/PT and severity. If a subject experiences multiple AEs of different severities, the most severe one will be used for calculation
- The number of events, number of subjects and incidence of AEs, AEs related to study drug, Grade \geq 3 AEs, Grade \geq 3 AEs related to study drug, SAEs and SAEs related to study drug will be calculated by PT
- Time of onset (Day) = start date of AE date of first dose + 1; duration (days) = end date of AE start date of AE + 1

 ◆ AEs, AEs related to study drug, Grade ≥ 3 AEs, SAEs, AEs leading to early withdrawal and AEs with unknown outcomes (persistent, aggravated, death, unknown) will be listed

6.5.2. Laboratory Tests

Based on SS, the clinical significance of subjects' laboratory tests (hematology, blood chemistry, urinalysis and coagulation function) before and after administration will be summarized using a shift table (judgment on clinical significance will be made based on the worst result after administration). The subjects' laboratory test results and changes from baseline will be descriptively analyzed by visit time point, with the latest test result before the first dose as the baseline.

• Laboratory test results of subjects with clinically significant abnormalities after administration will be listed

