of the trial, and appropriate treatment and handling measures should be adopted if necessary. In case of any abnormal indicator with clinical significance during the trial, the subjects should return to the hospital for re-examination as required by the investigator. After the investigator judges that the abnormal value becomes normal and the abnormality is not clinically significant or has become stable without the need for further tracking, they can be discharged.

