Examination Items and Time at the End of Run-in Period (D-1)	
Examination items at the end of the run-in period (D-1) include the following: Vital signs; physical examination; body weight measurement; hematology; blood biochemistry; urinalysis; four coagulation tests; Fibroscan; MRI-PDFF; blood pregnancy test (for females only); 12-lead ECG; urine drug screening; and alcohol breath test.
 
For patients with MRI-PDFF, Fibrocan, hematology, blood biochemistry, urinalysis, and four coagulation test reports within 7 days before the first dose (D-7–D-1), it will be unnecessary to perform these examinations again on D-1.

Inclusion Criteria	
Subjects are eligible for the study only if all of the following inclusion criteria are met:
 
 
1) Subjects aged <math>\geq 18</math> and <math>\leq 65</math>, male or female;
 
2) Body mass index (BMI) <math>\geq 25 \text{ kg/m}^2</math> at screening;
 
3) Subjects fulfilling the following criteria: 
 
a) ALT level exceeds the upper limit of normal once within 3 months (ALT elevation without other obvious reasons);
 
b) Mean liver fat content <math>\geq 10\%</math> during screening and at the end of the run-in period (MRI-PDFF);
 
 
 
4) Stable body weight (defined as weight gain or loss <math>\leq 5\%</math>) 4–8 weeks pre-dose;
 
5) Pre-dose blood pressure: Systolic blood pressure <math>\leq 160 \text{ mmHg}</math> and diastolic blood pressure <math>\leq 95 \text{ mmHg}</math> (oral antihypertensive drugs can be taken regularly);
 
6) Maintain the same medication and lifestyle (diet and/or exercise) as those at enrollment during the trial;
 
7) Subjects who have no birth plan from screening to 6 months after the last dose and voluntarily take reliable contraceptive measures;
 
8) Subjects who fully understand the purpose and requirements of the trial, voluntarily participate in the clinical trial, and sign the written ICF, and are able to complete all trial processes according to the trial requirements.
 

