	
randomized/enrolled subjects will be summarized. The number and percentage of subjects included in different analysis data sets will be calculated for each dose group.
 
Statistical Analysis of C-QTC Study:
 
Exploratory statistical analysis will be performed on C-QTc based on PK and QT interval changes. Descriptive analysis will be performed for QT/QTc intervals and changes from baseline at each time point, and line charts will be used to depict the changes at each time point and between groups. Baseline correction (<math>\Delta</math>QTc) and placebo correction (<math>\Delta\Delta</math>QTc) will be applied to the obtained QT/QTc intervals, with <math>\Delta</math>QTc as the dependent variable to measure the degree of drug effect on QT/QTc. The changes in drug concentration and QT/QTc intervals will be considered for model-based exploratory analysis.
 
Tolerability and Safety Evaluation:
 
Statistical analysis will be performed using SAS (v9.4 or above).
 
Adverse events (AEs) will be coded as per the Medical Dictionary for Regulatory Activities (MedDRA). The AEs observed during the trial will be described by system organ class (SOC) and preferred term (PT) for each dose group. Descriptive statistics of clinical laboratory tests, 12-lead ECGs, C-QTc study, vital signs, and physical examination results will be performed for each dose group. Clinically significant changes in clinical laboratory findings from baseline will be presented in the shift table.
 
Evaluation of the C-QTc study: The threshold of concern is a <math>\Delta\Delta</math>QTc interval prolongation exceeding 5 ms. Based on the C-QTc study results, it can be confirmed whether the conditions for conducting a TQT study are met. According to the C-QTc model, if the upper limit of two-sided 90% CI for <math>\Delta\Delta</math>QTcF corresponding to the highest clinical exposure is <math>\leq</math> 10 ms, it can be considered that the mean QT/QTc effect of the drug is not more than 5 ms, and the C-QTc study result is negative. However, if the upper limit of two-sided 90% CI for <math>\Delta\Delta</math>QTcF corresponding to low clinical exposure is <math>></math> 10 ms by model calculation, the C-QTc study result will be positive. When the upper limit of two-sided 90% CI for <math>\Delta\Delta</math>QTcF corresponding to low clinical exposure is <math>\leq</math> 10 ms and the upper limit of two-sided 90% CI for <math>\Delta\Delta</math>QTcF corresponding to the highest clinical exposure is <math>></math> 10 ms, the dose range for negative <math>\Delta\Delta</math>QTcF (<math>\leq</math> 10 ms) can be obtained with the model.
 
Pharmacokinetic Analysis:
 
Plasma concentrations will be summarized by dose group and scheduled sampling time point, including the number of subjects, the number of subjects below the quantification limit (BQL), arithmetic mean, standard deviation, coefficient of variation, median, minimum, maximum, geometric mean, and geometric coefficient of variation. Individual and mean plasma concentration-time (C-T) curves will be plotted separately.
 
Based on the non-compartmental model, Phoenix WinNonlin software (Certara USA Inc, version 8.2 or above) will be used to calculate PK parameters (main PK parameters include <math>T_{max}</math>, <math>C_{max}</math>, and AUC). PK parameters will be summarized by dose group, including the number of subjects, arithmetic mean, standard deviation, median, minimum, and

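### Laboratory safety is categorised only by a shift in clinical significance, so a subject already rated significant at baseline cannot worsen in the table, and no planned output counts subjects passing a liver-test threshold

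*SAP*

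**What the plan says.** SAP 6.5.2 plans three laboratory outputs on the Safety Set.

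- A before/after table of clinical significance: results "will be summarized using a shift table (judgment on clinical significance will be made based on the worst result after administration").
- Descriptive values and changes by visit, "with the latest test result before the first dose as the baseline".
- A listing of results for subjects with a clinically significant abnormality after dosing.

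The protocol synopsis (Statistical Analysis, Tolerability and Safety Evaluation) commits to the same table: "Clinically significant changes in clinical laboratory findings from baseline will be presented in the shift table". Neither text attaches a number to the categories. SAP 6.5.2 does not say who rates significance. Elsewhere the protocol gives that judgement to the investigator (Overall Design, on following up abnormal values: "After the investigator judges that the abnormal value becomes normal and the abnormality is not clinically significant").

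Entry is linked to ALT. Inclusion criterion 3a reads "ALT level exceeds the upper limit of normal once within 3 months (ALT elevation without other obvious reasons"), and no upper ALT limit appears in the inclusion or exclusion criteria.

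Four other parts of the SAP bear on the point. Section 6.1 sets the descriptive statistics and pools the placebo subjects. Section 6.4.3 treats ALT and AST as PD indicators, summarised and listed at baseline, D29 and D56. Sections 4.1 and 6.5.1 grade AEs by CTCAE 5.0 and tabulate them by severity. Section 6.5.7 sets numeric bands for QTc and for its change from baseline.

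**The concern.** A shift table shows worsening only if subjects start in a category that leaves room to move. This trial selects on a recent raised ALT, so some subjects may start in the worst category. For them the table looks the same whether ALT is stable or rises several-fold. A subject rated abnormal but not significant moves only if the rating changes.

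The continuous summaries do not supply a count. ALT and AST are also efficacy variables, and a fall is hoped for, so falls in most of a group can offset a rise in one subject when the mean is read.

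Safety and tolerability is the primary objective, and elevated AST was among the common possibly drug-related events in the single-dose Phase Ia trial (N=2, 3.4%). A reader would want to know how many subjects per dose group passed a stated liver-test level, compared with placebo. The plan does not produce that figure.

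**Working it through.** There is no stated figure to reproduce, so the check covers the cells of the table, the possible size of the affected subgroup, and what the other outputs would show.

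**1. The cells.** The post-dose category is the significance of the worst result.

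| Baseline rating | Worst post-dose ALT, rated significant | Move to a worse cell? |
|---|---|---|
| Significant | 2 × ULN | No |
| Significant | 4 × ULN | No |
| Significant | 8 × ULN | No |
| Significant | 20 × ULN | No |
| Not significant | 8 × ULN | Yes |

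From a significant baseline the only possible move is towards improvement.

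**2. How many subjects this could affect.** Each group has 9 active subjects (SAP 3.2). The share p rated significant at baseline is not in the documents, so p is an assumption. The expected number is 9p, and the chance of at least one is 1 − (1 − p)^9.

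| Assumed p | Expected of 9 | Chance of at least one |
|---|---|---|
| 10% | 0.9 | 1 − 0.9^9 = 61% |
| 30% | 2.7 | 1 − 0.7^9 = 96% |
| 50% | 4.5 | 1 − 0.5^9 = 99.8% |

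**3. What the continuous summary would show.** The ALT values here are illustrative. Of 9 active subjects, eight go from 80 to 60 U/L and one goes from 80 to 240 U/L.

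- Mean after dosing: (8 × 60 + 240)/9 = 720/9 = 80.0, so the mean change is 0.0.
- Median change: −20.
- SD of change: √[(8 × 20² + 160²)/8] = √3600 = 60.
- Maximum change: +160, which is 160/80 = +200% of baseline.
- Count at or above 3 × own baseline: 1/9 = 11.1%. No planned output reports this.

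The mean hides the event. The SD and the maximum, both required by SAP 6.1, do not.

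**4. Comparison with QTc.** SAP 6.5.6 plans the same kind of significance shift table for the ECG, and 6.5.7 then adds numeric bands: QTc above 450, 480 and 500, and a change of at least 30 or 60. SAP 6.5.2 has no counterpart for any liver test: no multiple of ULN, no multiple of baseline, no laboratory grade, and no joint display of ALT and bilirubin.

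**The case against.** The strongest case against the point is that a liver event would be seen anyway, and much of that stands. In the example the subject is rated significant after dosing and so enters the SAP 6.5.2 listing. SAP 6.4.3 lists ALT and AST for all enrolled subjects at baseline, D29 and D56, whatever the rating. The maximum change is reported. A rise reported as an AE is graded and appears in the severity tables of SAP 6.5.1. With nine active subjects per group, reading a listing is practical. A reader might infer that a real liver injury could pass unnoticed, or that only the maximum would hint at it; the documents do not support that.

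A reader might also infer that the entry criterion saturates the scale. That is not shown. Criterion 3a needs one raised value within three months, while baseline is the latest pre-dose result, taken after a run-in of four to eight weeks. That value may be normal, or abnormal without being rated significant, and in either case worsening can register. Nor do the documents show that raters will discount raised enzymes. The Phase Ia AST events were Grade 1, so they illustrate relevance, not a signal.

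Three things remain. The 6.5.2 listing and the AE route both depend on a rating or a report, and neither document says that a further rise from an already significant baseline must be reported as an AE. The 6.4.3 listing omits bilirubin and has no worst-value category. No output gives a count by threshold. The mock shells named in SAP section 7 were not available, so table layouts there could not be checked.

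**Conclusion.** The point holds as a gap in summarisation. Laboratory results are categorised only by a shift in clinical significance, a subject rated significant at baseline cannot move to a worse cell, and no planned table counts subjects passing a liver-test threshold by dose group against pooled placebo. It is not a failure to detect, because individual values, extremes and graded AEs are already planned.

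The number of subjects affected is unknown. The range of 0.9 to 4.5 of 9 rests on assumed shares of 10% to 50%, and the ALT example on assumed values. The gap itself rests only on the text of SAP 6.5.2 and the protocol synopsis. Given the primary safety objective, the population and the SAP's own practice for QTc, closing it is a worthwhile, low-cost improvement.

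**What to change.** Keep the clinical-significance shift table, since the protocol commits to it and removing it would put the SAP in conflict with the protocol. Add to SAP 6.5.2:

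- A table, by dose group and pooled placebo (3 × 4 = 12 to 3 × 5 = 15 subjects), of each subject's worst post-dose ALT, AST and bilirubin in pre-set multiples of own baseline (for example at least 2, 3 and 5 times) and of ULN. Include ALP if it is in the biochemistry panel; the supplied text does not list the panel.
- A per-subject display of peak ALT against peak bilirubin.

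Fix the cut-points before unblinding. The cost is one or two extra tables or displays from the planned safety biochemistry, with no new visits. The downside is that some transient elevations will be displayed that the current table would not show.
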